	Group 2b	10
Group 3	Group 3a	10
	Group 3b	10
Total		60

	
It is to be noted that the 1:1 ratio per subgroup is unlikely to hold as only subjects dengue seropositive at baseline will be eligible to booster injection.
																											

Schedule of Study Procedures:
	
STAGE I:
 
Vaccination
 
All subjects (N=1050) will receive 1 injection at Day 0, Day180 and Day 365: a total of 350 subjects will receive 3 doses of CYD dengue vaccine (Group 1); 350 subjects will receive 1 placebo injection followed by 2 doses of CYD dengue vaccine (Group 2); and 350 subjects will receive 2 placebo injections followed by 1 dose of CYD dengue vaccine (Group 3).
 
Blood Sampling
 
All subjects will provide a blood sample at enrollment Visit 1 (V01; pre-injection 1, BL1), at V03 (pre-injection 2, BL2) at V04 (V03 + 28 days, BL3), at V05 (pre-injection 3, BL4), at V06 (V05 + 28 days, BL5), and at Year 1 (Y1) V07 (V05 + 12M, BL6) for dengue immunogenicity.
 
Note: AIT subset is described below.
 
Table S8: STAGE I injection and blood sampling schedules
 
  
 Procedure	Product or Test	V01 (D0)	V02 (V01+ 28d)	V03 (V01+ 6M)	V04 (V03+ 28d)	V05 (V01+ 12M)	V06 (V05+ 28d)	Y1 V07 (V05+ 12M)	
   
 Injection	CYD or PLA	Inj. 1	Contact visit	Inj. 2		Inj. 3			
 
 Collection of blood sample:	Neutralizing Abs (all subjects)	BL1* (pre-inj. 1) 5 mL	N/A	BL2* (pre-inj. 2) 5 ml	BL3 5 mL	BL4* (pre-inj. 3) 5 mL	BL5 5 mL	BL6† 5 mL	
  
 
* Dengue status at baseline will be assessed for each group prior to the first CYD injection (Group 1 at V01, Group 2 at V03, and Group 3 at V05)
 
† In the context of STAGE I, BL6 will be used to assess neutralizing Abs persistence at 1 year post last primary series injection. In STAGE II, BL6 will be used to assess neutralizing Ab levels at pre-booster injection for subjects from subgroup a that were seropositive at baseline
 
D or d=day; M=month; N/A=not applicable
 
STAGE II:
 
Vaccination
 
It is estimated that between 60% (N=630) and 70% (N=735) of the initial number of subjects (N=1050) will be eligible to receive a CYD booster dose at Y1 or Year 2 (Y2).
 
 • approximately 315 to 367 subjects will receive a CYD booster dose at Y1 post STAGE I last dose (Groups 1a, 2a, 3a) • approximately 315 to 367 subjects will receive a CYD booster dose at Y2 post STAGE I last dose (Groups 1b, 2b, 3b). 
Blood Sampling
 
All subjects will provide a blood sample 1 year post last injection (BL6; to assess Ab persistence as part of STAGE I; and pre-booster Ab levels in subgroup a as part of STAGE II). In addition, subgroup a will provide a blood sample 28 days after receiving the booster injection (BL9). Subjects from subgroup b identified as seropositive at baseline will provide blood samples immediately before (BL10) and 28 days after (BL13) receiving the booster injection.
	Procedure	Product or Test	V01 (D0)	V02 (V01+ 28d)	V03 (V01+ 6M)	V04 (V03+ 28d)	V05 (V01+ 12M)	V06 (V05+ 28d)	Y1 V07 (V05+ 12M)	Injection	CYD or PLA	Inj. 1	Contact visit	Inj. 2		Inj. 3			Collection of blood sample:	Neutralizing Abs (all subjects)	BL1* (pre-inj. 1) 5 mL	N/A	BL2* (pre-inj. 2) 5 ml	BL3 5 mL	BL4* (pre-inj. 3) 5 mL	BL5 5 mL	BL6† 5 mL

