 - 13) **For AIT subset only (60 subjects):** an additional volume of blood will be drawn (25 mL for adolescents and 35 mL for adults) to assess CMI (see [Section 7.1.2](#) for detailed instructions regarding the handling of CMI blood samples)

It is important to note that, if the attempt(s) to collect blood is (are) unsuccessful, the subject should be given the opportunity for another attempt, even on another day. If ultimately a blood sample cannot be obtained, the reason will be recorded in the eCRF. In that case, and if the subject wants to participate in the trial, he/she will be vaccinated.

- 14) Inject the appropriate study vaccine
- 15) Record the date of injection, the site and side of injection and the route of administration, as well as the dose number of the vaccine
- 16) Affix the vaccine labels in the subject's source documents
- 17) Keep the subject under observation for 30 minutes, and record any adverse reaction in the source documents
- 18) Give the subject / subject's parent (s) / legally acceptable representative(s) the diary card 1 (DC1) to record any injection site reactions and systemic AEs, together with

^a To be considered of non-child-bearing potential, a female must be post-menopausal for at least 1 year, surgically sterile, or using an effective method of contraception or abstinence from at least 4 weeks prior to vaccination and until at least 3 weeks after vaccination

instructions for its completion, including explanations on the definition and use of intensity scales for collection of AEs (Remind the parent / legally acceptable representative to bring back the DC when they return for Visit 02 at a specified date)

- 19) Give the subject / subject's parent (s) / legally acceptable representative(s) a ruler to measure the size of any injection site reaction and a thermometer for temperature measurement, and instructions on how to use them
- 20) Remind the subject / subject's parent (s) / legally acceptable representative(s) to call the study center if a serious medical event occurs
- 21) Arrange an appointment for the second visit (28 days [+ 14 days])
- 22) Complete the source documents and relevant eCRF pages for this visit

The visit may be postponed once if the subject is temporarily not eligible at Visit 1

Visit 2 (28 days [+14-day time window] after Visit 1): Collection of Safety Information

The Investigator or designated study personnel will:

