6.5 Randomization and Allocation Procedures

Each subject who meets the inclusion/exclusion criteria and signs an ICF/AF will be randomly assigned to one of the 3 groups (6 subgroups) via an IVRS / IWRS, according to a 1:1:1:1:1:1 enrollment ratio (350 subjects per group [175 subjects per subgroup]).

Site staff will call or connect to the IVRS/IWRS, enter identification and security information, and confirm a minimal amount of data in response to IVRS/IWRS prompts. The IVRS/IWRS will then state the subject number and the vaccine assignment (code number). Subject numbers will be

^a according to local regulations

recorded on the eCRFs and will not be reassigned for any reason. The full detailed procedures for randomization are described in the Operating Guidelines.

Sixty subjects from a specific site in Colombia who consent to participation in additional immune response testing will be selected for the AIT subset.

Subject numbers will be 8 digits long, with a 3-digit center identifier and a 5-digit subject identifier. The first digit of the subject identifier will be a pre-defined figure (0 or 1); “1” will be used for subjects assigned to the AIT subset and “0” for all other subjects. The second digit of the subject identifier will be a pre-defined figure (1 or 2); “1” will be used for subjects randomized to subgroup “a” (receive booster at 1 Year) and “2” for subjects randomized to subgroup “b” (receive booster at 2 Years). For example, Subject 001-12001 will be the first subject randomized to the AIT subset enrolled in center number 1 and will receive the booster at 24 months (Y2) following administration of the third dose in the primary series.

Randomization will be performed with permuted block method with stratification by site and age group. Age group categories will be:

- Children 9 through 11 years of age
- Adolescents 12 through 17 years of age
- Adults 18 through 39 years of age
- Adults 40 through 50 years of age

A double randomization system will be used, this implies that the subject treatment allocation will be separated from doses dispensing. Each dose will have both a code number and a dose number. The code number will be used by the IVRS/IWRS while the dose number will be entered in the eCRF. The unique dose numbers will be defined according to a random list to ensure that dose numbers cannot be used to distinguish between treatment groups.

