9.1.1.2 Immunogenicity Assessment Methods

Dengue Neutralizing Abs

Dengue neutralizing Ab levels will be measured (using parental dengue virus strains of CYD dengue vaccine constructs) by Sanofi Pasteur GCI, Swiftwater, USA (or outsourced with a GCI selected external laboratory).

Dengue PRNT

Serial, 2-fold dilutions of serum to be tested (previously heat-inactivated) are mixed with a constant challenge dose of each dengue virus serotype 1, 2, 3 or 4 (expressed as plaque forming unit [PFU]/mL). The mixtures are inoculated into wells of a microplate with confluent Vero cell monolayers. After adsorption, cell monolayers are incubated for a few days. The presence of dengue virus infected cells is indicated by formation of plaques. A reduction in virus infectivity due to neutralization by Ab present in serum samples is detected. The reported value (end point neutralization titer) represents the highest dilution of serum at which $\geq 50\%$ of dengue challenge virus (in plaque counts) is neutralized when compared to the mean viral plaque count in the negative control wells which represents the 100% virus load. The end point neutralization titers are presented as discontinuous values. The lower limit of quantitation (LLOQ) of the assay is 10 (1/ dil).

For STAGE I, all subjects will provide blood samples for assessing neutralizing Ab titers against each of the 4 parental dengue virus strains at baseline V01 (pre-Injection 1, BL1), at V03 (pre-Injection 2, BL2) at V04 (V03 + 28 days, BL3), at V05 (pre-Injection 3, BL4), at V06 (V05 + 28 days, BL5), and at Y1 V07 (1 year post-Injection 3, BL6) for dengue immunogenicity.

For STAGE II, subjects will provide blood samples for assessing neutralizing Ab titers against each of the 4 parental dengue virus strains. The first blood sample will be collected in all subjects approximately 1 year post last primary series injection (BL6; to assess Ab persistence but also pre-booster Ab levels in subgroup a). Subjects receiving the booster injection will provide additional blood samples. Subjects from subgroup a will provide a blood sample 28 days after receiving the booster injection (BL9). Subjects from subgroup b will provide blood samples immediately before booster injection (BL10) and 28 days after booster injection (BL13).

Additional assays and other analyses might be used to assess and characterize dengue immune response if required.

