5.1.1.2 Statistical Methods

STAGE I:

The non-inferiority tests will be performed using the two sample t-test 95% 2 sided CI of the difference of the means of the log₁₀ transformed post-vaccination titer between Group 2 and Group 1 ($\alpha=2.5\%$ one sided) at 28 days and 1 year after last injection. For each serotype, non-inferiority will be demonstrated if the lower limit of the two sided adjusted 95% CI is greater than 1/2 (i.e., the log 10 of the difference should be above -0.301).

STAGE II:

Paired Test (Within Group 1)

The non-inferiority tests will be performed using the paired t-test adjusted 95% 2 sided CI ($100*[1 - \alpha/\text{total number of overall hypothesis tests to perform in STAGE II}]$ CI [Bonferonni adjustment to control for multiplicity]) of the difference of the means of the log₁₀ transformed post-vaccination titer between booster j and post Dose 3 j ($\alpha=2.5\%$ one sided). For each serotype, non-inferiority will be demonstrated if the lower limit of the 2-sided adjusted 95% CI is greater than 1/2 (i.e., the log 10 of the difference should be above -0.301). Subjects with non-missing post dose 3 and post booster titer will be included in this analysis.

Two Sample Test (Between Group 1 and Group 2)

The non-inferiority tests will be performed using the two sample t-test adjusted 95% 2 sided CI ($100*[1 - \alpha/\text{total number of overall hypothesis tests to perform in STAGE II}]$ CI [Bonferonni adjustment to control for multiplicity]) of the difference of the means of the log₁₀ transformed post-vaccination titer between Group j and Group 1 ($\alpha=2.5\%$ one sided). For each serotype, non-inferiority will be demonstrated if the lower limit of the two sided adjusted 95% CI is greater than 1/2 (i.e., the log 10 of the difference should be above -0.301).

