5.1.2.2 Statistical Methods

5.1.2.2.1 Statistical Methods for Hypotheses Objectives

STAGE I:

The superiority tests will be performed using the two sample t-test 95% 2 sided CI of the difference of the means of the log10 transformed post-vaccination titer between Group 2 and Group 1 ($\alpha=2.5\%$ one sided) at 28 days and 1 year after last injection. For each serotype, superiority will be demonstrated if the lower limit of the two sided adjusted 95% CI is greater than 1 (i.e., the log 10 of the difference should be above 0).

STAGE II:

Paired Test (Within Group 1)

The superiority tests will be performed using the paired t-test adjusted 95% 2 sided CI ($100*[1-\alpha/\text{total number of overall hypothesis tests for non-inferiority to perform in STAGE II}]$ CI [Bonferonni adjustment to control for multiplicity]) of the difference of the means of the log10 transformed post-vaccination titer between booster j and post Dose 3 j ($\alpha=2.5\%$ one sided). For each serotype, superiority will be demonstrated if the lower limit of the two sided adjusted 95% CI is greater than 1 (i.e., the log 10 of the difference should be above 0). Subjects with non-missing post dose 3 and post-booster titer will be included in this analysis.

Two Sample Test (Between Group 1)

The superiority tests will be performed using the two sample t-test adjusted 95% 2 sided CI ($100*[1-\alpha/\text{number of overall hypothesis tests for non-inferiority to perform in STAGE II}]$ CI [Bonferonni adjustment to control for multiplicity]) of the difference of the means of the log10 transformed post-vaccination titer between Group j and Group 1 ($\alpha=2.5\%$ one sided). For each serotype, superiority will be demonstrated if the lower limit of the two sided adjusted 95% CI is greater than 1 (i.e., the log 10 of the difference should be above 0).

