5.5 Determination of Sample Size and Power Calculation

[figure not shown]
A total of 1050 subjects are planned to be enrolled with a 1:1:1 enrollment ratio (350 per group [or 1:1:1:1:1:1 randomization ratio, 175 per subgroup]).

[REDACTED]

Table 5.2: Power of the study based on the Primary Objectives - STAGE I

Baseline Seropositive (%)	Population per group	Objectives	Endpoints	NI Margin	Power (%)
100%	296	Group 2 vs Group 1	28 days post-Inj 3 vs 28 days post-Inj 3	2	99.52
	296	Group 2 vs Group 1	1year post-Inj 3 vs 1 year post-Inj 3	2	95.20
90%	266	Group 2 vs Group 1	28 days post-Inj 3 vs 28 days post-Inj 3	2	98.94
	266	Group 2 vs Group 1	1year post-Inj 3 vs 1 year post-Inj 3	2	93.26
80%	235	Group 2 vs Group 1	28 days post-Inj 3 vs 28 days post-Inj 3	2	97.76
	235	Group 2 vs Group 1	1year post-Inj 3 vs 1 year post-Inj 3	2	89.22
70%	207	Group 2 vs Group 1	28 days post-Inj 3 vs 28 days post-Inj 3	2	95.78
	207	Group 2 vs Group 1	1year post-Inj 3 vs 1 year post-Inj 3	2	83.54
60%	178	Group 2 vs Group 1	28 days post-Inj 3 vs 28 days post-Inj 3	2	92.92
	178	Group 2 vs Group 1	1year post-Inj 3 vs 1 year post-Inj 3	2	75.64

Table 5.3: [REDACTED]

The following assumptions were considered:

- Alpha level of 2.5% (one sided) with a Bonferonni adjustment for multiplicity in Stage II
- Non-inferiority margin of 2 ($\log_{10} = 0.301$)

- [REDACTED]

- Dropout rate of 15%

The sample size will also provide a 95% probability of observing an AE that has a true incidence of $>0.85\%$ in each group (N=350).

For the measurement of the Cellular Immune Response, a convenience number of 60 subjects from a specific site in Colombia who consent to participate in additional immune response testing, the AIT subset, was selected, 10 subjects from each subgroup.

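### The Stage I tests of Group 2 against Group 1 leave the BL1 titre and the stratification factors unused: a valid analysis, but one that may give up precision, mainly at 1 year

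*SAP*

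**What the plan says.** SAP 5.1.1.2 on the Stage I primary comparison: "The non-inferiority tests will be performed using the two sample t-test 95% 2 sided CI of the difference of the means" of log10 post-vaccination titre, Group 2 against Group 1, at 28 days and at 1 year. Protocol 12.1.1 names the same test. The Stage I superiority tests follow the same form in SAP 5.1.2.2.1: "The superiority tests will be performed using the two sample t-test 95% 2 sided CI of the difference of the means" (also Protocol 12.1.2). No covariate is named. The word adjusted, applied to the interval in these sections, has no covariate attached and fits only multiplicity.

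The information left out is already planned:

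- Protocol 6.5: "Randomization will be performed with permuted block method with stratification by site and age group". There are four age groups and six sites.
- Protocol 9.1.1.2, on Stage I sampling: "all subjects will provide blood samples for assessing neutralizing Ab titers against each of the 4 parental dengue virus strains at baseline V01".
- BL1 can be missing. If blood cannot be drawn at Visit 1, Protocol 5.1.4 says: "In that case, and if the subject wants to participate in the trial, he/she will be vaccinated".

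The SAP does use ANCOVA elsewhere (5.1.3.1.1), but the Stage I model compares age strata at 28 days after injection 3 and has no group term. Stage I group contrasts are otherwise only described by GMR (5.1.3.1). Under SAP 5.1.1.1, all four serotypes must pass at each time point, and only the 28-day result opens the Stage II tests against Group 2.

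**The concern.** Part of the between-subject spread in titres may be predictable from the pre-injection titre, age and site. An unadjusted comparison leaves that spread in the error term, so the interval may be wider than it needs to be.

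The 28-day test has power to spare. The 1-year test has less: at the lower end of the seropositive share that the protocol expects, its stated power is below 80%. A covariate that the trial already measures could narrow that interval with no new samples.

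The ANCOVA in SAP 5.1.3.1.1 cannot simply be given a group term. Its baseline is the group-specific one of SAP 4.4.1.4.2: BL1 in Group 1, but BL2 in Group 2, drawn six months after randomisation.

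**Working it through.** **The plan's own figures.** The relevant table is "Table 5.2: Power of the study based on the Primary Objectives - STAGE I". At 60% and 70% seropositive, 296 × 0.60 = 177.6 and 296 × 0.70 = 207.2, which give its 178 and 207 per group. Stated power at 178, 207, 235, 266 and 296 per group is:

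- 1 year: 75.64, 83.54, 89.22, 93.26, 95.20%
- 28 days: 92.92, 95.78, 97.76, 98.94, 99.52%

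The SD is not visible, so these cannot be reproduced independently. As a consistency check, one SD (0.92 log10, two equally limiting independent serotypes, true ratio 1, one-sided 2.5%) fits all five 1-year values to within 2 points. The same SD at one-sided 1.25% fits the protocol's Table 12.1 equally well. The two tables therefore agree, apart from the Stage I Bonferroni split that the SAP removed.

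**How many will be evaluable.** The protocol synopsis says: "It is estimated that between 60% (N=630) and 70% (N=735) of the initial number of subjects (N=1050) will be eligible", and then "approximately 315 to 367 subjects will receive a CYD booster dose at Y1 post STAGE I last dose". If these counts are already net of dropout, there are 630/3 = 210 to 735/3 = 245 per group. Interpolating, 83.54 + (3/28) × 5.68 = 84.15% and 89.22 + (10/31) × 4.04 = 90.52%. This reading implies 210/297.5 = 71% to 245/297.5 = 82% seropositive among those retained (350 × 0.85 = 297.5). If the 15% dropout still has to come off, 178-207 applies.

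**Effect of adjustment.** Effective n = n / (1 − r²) / 1.015, read off Table 5.2 by linear interpolation (first segment extended below 178). Assumptions: one r for all serotypes; site and age uninformative. The 1.015 is the variance cost of 9 extra terms (1 titre, 3 age, 5 site), from a simulation with 350 per arm, blocks of 4 in 24 strata and 51% of subjects kept. Example: 178 / 0.91 / 1.015 = 192.7, giving 75.64 + (14.7/29) × 7.90 = 79.6%.

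| Net power (%) | r = 0.1 | 0.2 | 0.3 | 0.4 | 0.5 |
|---|---|---|---|---|---|
| 1 year, 178 per group | 75.4 | 76.9 | 79.6 | 83.9 | 89.0 |
| 1 year, 207 | 83.3 | 84.6 | 87.0 | 90.2 | 93.6 |
| 1 year, 210 | 83.9 | 85.3 | 87.7 | 90.7 | 93.9 |
| 1 year, 245 | 90.4 | 91.4 | 93.2 | 94.6 | above 95.2 |
| 28 days, 178 | 92.8 | 93.4 | 94.4 | 95.9 | 97.7 |

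Break-even is r = √0.015 = 0.12. At 178 per group, 80% needs an effective 194.0, so r = √(1 − 178/(194.0 × 1.015)) = 0.31; 90% needs 241.0, so r = 0.52.

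A noncentral-t check (four independent serotypes, SD 0.82 solved from 75.64%) gives 75.3, 77.5, 81.1, 85.9 and 91.2% for the first row, and 74.5% at r = 0, a loss of about 1 point.

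**Validity of the planned test.** Simulation with 24 strata, 192 per group and 3,000 runs put one-sided type I error at 1.9-2.4% for the t-test and 2.2-2.8% for ANCOVA.

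**Side effect of a plain BL1 covariate.** Group 2 is selected on BL2, so a subject infected between V01 and V03 enters Group 2 only, with BL1 below LLOQ for all serotypes. Across 24 assumed scenarios (30-40% seronegative, 3-10% infected per year, slope 0.3-0.5, new infections responding equally, 3-fold lower or 3-fold higher), plain adjustment moves the ratio towards Group 2 by 0.002-0.018 log10 relative to the t-test. At 0.018, with SE = 0.82 × √(2/178 × 0.75 × 1.015) = 0.0758, one-sided error at the margin is 1 − Φ(1.96 − 0.018/0.0758) = 4.2%. With the covariate rule under the fix, the ANCOVA stays within about 0.001 of the t-test.

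**What that agreement does not show.** The same selection reaches the t-test. With 40% seronegative and 10% infected per year over half a year, newly infected subjects are 0.02/0.62 = 3.2% of Group 2. If they respond 3-fold differently, the unadjusted difference moves by 0.032 × 0.477 = 0.015 log10.

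**The case against.** The strongest objection is that nothing requires adjustment. The t-test matches the stated GMT-ratio hypothesis, and the gain cannot be known from the documents: no correlation is given, and the 1-year sample is about 24 months after BL1, so r may be low. Below r of about 0.12 the change costs power. At 28 days power is already 92.92-95.78%, and only that test opens Stage II. All of this stands, and it limits the point to an option worth weighing.

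The proposed covariate rule also conflicts with the plan, which does not impute missing immunogenicity data (SAP 5.3.1, Protocol 12.3.1) and sets titres below LLOQ to half of LLOQ for GMTs (SAP 4.4.1.1). That stands too, so the rule has to be declared as an exception. It also rests on simulation inputs that are not in the documents.

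Timing may decide the matter. Inclusion was planned to end in August 2016; adding the V05 and V07 windows puts the last 1-year sample at about November 2018, and the SAP text refers to March 2019. The date of the first lock is not given.

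A reader might infer that the unadjusted test is biased or inflates type I error. The documents do not support this: omitting stratification factors leaves the t-test valid and, in simulation, slightly conservative. A reader might also infer that the 1-year objective is underpowered. That holds against an 80% benchmark only at 178 per group; the protocol's own eligible counts can equally mean 84-91%.

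**Conclusion.** The point holds as one of efficiency, worth considering, with medium confidence. The Stage I group comparisons use none of the planned baseline information, and the cost falls mainly on the 1-year test. At 178 per group the net change runs from about −0.2 points at r = 0.1 (75.4 against 75.64%) to about +13 at r = 0.5 (89.0%). At 245 per group with r up to 0.4 it is at most about +4 (94.6 against 90.5%). At 28 days and 178 per group it is at most about +5 (97.7 against 92.92%).

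These figures rest on an assumed common r, on uninformative site and age, and on interpolation of the SAP's table. That information is unused is certain; how much it is worth is not.

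Valid here describes the test statistic. Fixing serostatus at BL1 in one group and BL2 in the other is a separate matter that can shift either analysis, by about 0.015 log10 under the assumptions shown (5% of the 0.301 margin).

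**What to change.** Before the first unblinded analysis, replace the Stage I test in SAP 5.1.1.2 by a per-serotype ANCOVA at 28 days and at 1 year:

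log10 titre = group + log10 BL1 titre of the same serotype + age group (4 levels) + site (6 levels)

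Use BL1 in both groups, not the group-specific baseline of SAP 4.4.1.4.2. Keep the margin and the 95% interval rule.

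- **Covariate rule.** Where BL1 is missing, or below LLOQ for all four serotypes, set the covariate (only) to the pooled mean log10 BL1 of the other subjects for that serotype. By the serostatus definitions, the all-below-LLOQ case can arise only in Group 2. State the rule in SAP 5.3.1 and 4.4.1.1 and Protocol 12.3.1 as an explicit exception to the no-imputation and half-LLOQ rules. Outcome titres remain unimputed.
- **Superiority.** Use the same model for the Stage I superiority tests in SAP 5.1.2.2.1, with analysis sets and alpha unchanged.
- **Sensitivity analyses.** Keep the t-test. Also repeat the ANCOVA in subjects seropositive on BL1 in both groups, because agreement between t-test and ANCOVA cannot reveal the serostatus shift. Leave the primary-set and booster-eligibility definitions, and the Stage II tests, as they are.
- **Declaration.** Record the change in SAP 5.7 or in a protocol amendment, since Protocol 12.1.1 and 12.1.2 name the t-test. If the 1-year database is already unblinded, report the ANCOVA as supportive only.

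The cost is these text edits, two sensitivity runs, and about 1 point of power if all covariates are uninformative. No new samples or assays are needed.
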